Peripheral Visual Field Test - Since the Humphrey visual field test only measures up to 30° in the periphery, an additional peripheral visual field test will be administered using a semi-circular frame device (fig. 1) set 50 cm in front of the subject with LED lights acting as visual stimulus, located at azimuths of 15°, 30°, 45°, 60°, and 75°, as well as a center fixation light. Lights will be presented at a random time with a fixation period between each trial and locations selected randomly. Subjects will be asked to fixate on the center fixation light while lights are presented at random locations at random times (0-1.5 seconds). Upon detecting a light, subjects will press a button. Subject responses will be used to determine how far in the periphery, up to 75°, a subject can see. The test will present a total of 5 trials at each location in both the intact and hemianopic side, as well as 5 trials with no stimuli.

This test uses the free-field frame device to position visual and auditory stimuli, in the form of LED lights and speakers, at different angles of the patient. The patient is asked to maintain visual fixation on a lit LED light straight ahead during the test. Speakers will play a brief burst of white noise from a random location 15° or 45° on either the left or right side. The subject will be asked to identify where the sound is originating from either verbally or using a button response pad. During this test, subjects' eyes may be videotaped or photographed. These recordings or photos will be reviewed by a member of the study team to confirm the subject is able to properly maintain visual fixation.

Figure 1: Free-field frame device

track rehabilitation progress. The test consists of 30 trials with visual stimulus presented either 15°, 30°, 45° in either the hemianopia field or the intact field at random time intervals.

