During this visit, baseline measurements for subjects will be obtained. Subjects will undergo a peripheral visual field test and be asked to complete 2 quality of life questionnaires: the National Eye Institute Visual Function Questionnaire (NEI VFQ-25) and the Veterans Affairs Low Vision Visual Function Questionnaire (VA LV VFQ-48). Subjects are expected to spend up to 2 hours for this visit.

(Optional) Study Session 2: Pre-Intervention Test - Humphrey Visual Field Test (1 hour)

Subjects will report to an optometrist, who will administer the Humphrey Visual Field Test, using a size V stimulus. This visit will be separate from the other pre-intervention tests due to the special equipment needed for the Humphrey Visual Field Perimetry. This visit is expected to take up to 1 hour. This visit may be omitted if subjects have a recent Humphrey Visual Field Perimetry test result and gives the study team permission to view and keep a copy of the result.

Study Sessions 3 – 32: Cross-Modal Rehabilitation Training (30 minutes each day)

Each cross-modal rehabilitation training session will take place either on the Wake Forest Baptist Medical Center Campus or in subjects' homes, if subjects find traveling to the Wake Forest campus to be too difficult to do daily. For patients who are performing rehabilitation at home, the study team will regularly call and check-in with the subject in order to make sure the patient is not experiencing any problems. The VR rehabilitation system will send data such as duration of rehabilitation and progress test results through a cellular network, in order to monitor compliance and track rehabilitation progress. The data will only be linked to a study identifier to maintain privacy. Initial rehabilitation sessions will be done at the Wake Forest Baptist Medical Center campus to ensure subjects understand how to use the rehabilitation device and are capable of performing rehabilitation at home.

In each rehabilitation session, subjects will sit down, put on a virtual reality headset with a pair of headphones, and use a button on a handheld controller to interact with the rehabilitation system. In order to make sure subjects are correctly performing rehabilitation, the headset may be outfitted an eye tracking system consisting of a camera and low intensity infrared lights to collect data on patient's eye movements.

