The virtual reality headset and headphones will provide visual and auditory stimulation used in the rehabilitation training. Each rehabilitation session will consist of 200 trials. At the end of each rehabilitation session, subjects will perform a brief 2-minute VR visual field progress test with the VR system to track rehabilitation progress. The rehabilitation will be considered complete once patients can reliably detect stimuli 45° in the hemianopic field.

If patients cannot detect stimuli at 15° by the end of 30 days of rehabilitation, they will repeat the rehabilitation for one more month, in order to determine if the slow progress or lack of progress is caused by simply not spending enough time performing rehabilitation.

Study Session 63: Post Rehabilitation Tests - Subject visual field did not increase (1 hour)

If no visual field improvement (measured by virtual reality visual field progress tests) has occurred at the end of the 2nd round of rehabilitation, subjects will complete one last visit, where they will be given the

NEI VFQ-25 and VA LV VFQ-48 questionnaires to complete. This visit will occur on the Wake Forest Baptist Medical Center campus.

Study Session 33: Post Rehabilitation Tests - Subject visual field increase (1.5 hours)

If a subject shows visual field expansion in the virtual reality visual field progress test, subjects will be given a **Peripheral Visual Field Test, NEI VFQ-25 and VA LV VFQ-48 Questionnaires** in order to measure visual field expansion and improvements in quality of life.

In previous animal studies, rehabilitated hemianopic animals could only detect spatial frequencies of 2 cycles/degree compared to over 5 cycles/degree in the (normal) intact animals. We hypothesize the subcortical visual pathway mediating the restored visual functions may not have the same capabilities as the visual cortex it is replacing. Therefore, recovered vision may have lower visual acuity. The different pathways involved in cross-modal rehabilitation may also affect abilities for shape recognition in the newly recovered visual field. We will explore whether this is the case with a simple **shape recognition test, visual acuity test, and color vision test** during this visit. Subjects will complete this visit on the Wake Forest Baptist Medical Center campus.

Study Session 34: Humphrey Visual Field Post-Intervention Test (1 hour)

Subjects will report to an optometrist for a **Humphrey Visual Field** perimetry test.

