from travel. Patients who perform any rehabilitation session at home will be provided with a phone number on which a member of the research team could be contacted during working hours if they need any advice or if the equipment fails. If needed, a study team member will also be available to visit patients' homes to help set-up the rehabilitation system and troubleshoot any issues.

To encourage continued participation, subjects will also be allowed to miss up to 3 consecutive rehabilitation sessions without affecting the course of rehabilitation in the first 2 weeks. If subjects do miss over 3 consecutive sessions, the 30 days of rehabilitation will be restarted. The days since the start of rehabilitation will be reset to 0 once rehabilitation restarts, and the event will be noted. This will be explained to subjects before the start of rehabilitation. Subjects will be allowed the chance to restart the rehabilitation twice before being excluded for noncompliance. If subjects cannot do rehabilitation treatments for more than 5 consecutive days and cannot be contacted, they will be withdrawn from the study and considered lost to follow-up.

Informed Consent

Signed informed consent will be obtained from each subject prior to the start of any interventions. The consent form will be written in plain language so that individuals will be able to understand the information in the consent form. In addition to providing individuals with a consent form, members of the research team will verbally outline each aspect of the consent form with subjects to make sure each subject understands the study requirements, purpose, and potential risks and benefits. If the subject has any questions, they will be referred to the investigator for answers. Consent will be obtained within the Wake Forest Baptist Medical Center by members of the study team.

Confidentiality and Privacy

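### The VR progress test routes subjects and is a secondary outcome, but it has no pre-training run and no no-light trials, so spared vision or guessing can be read as expansion on it

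*Combined protocol and SAP*

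**What the plan says.** All references are to the combined protocol and SAP.

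- **Timing.** Study Sessions 3 – 32: "At the end of each rehabilitation session, subjects will perform a brief 2-minute VR visual field progress test". Each session has 200 training trials, so the first VR run, at session 3, comes after 200 of them.
- **Baseline.** Study Session 1: "Subjects will undergo a peripheral visual field test and be asked to complete 2 quality of life questionnaires". Study Session 2 adds the Humphrey test. Neither lists a VR run.
- **Content.** "The test consists of 30 trials with visual stimulus presented either 15°, 30°, 45° in either the hemianopia field or the intact field". The layout separates this sentence from the Virtual Reality (Visual Field) Progress Test entry; I read it as completing that entry. The Peripheral Visual Field Test, by contrast, has 5 trials at each location "as well as 5 trials with no stimuli".
- **Use for routing.** Study Session 33: "If a subject shows visual field expansion in the virtual reality visual field progress test", the subject gets the frame test, the questionnaires and the shape, acuity and color tests, then Humphrey at session 34. A subject with no VR improvement after a second round gets session 63, which lists questionnaires only. The second round is triggered by an absolute level: "If patients cannot detect stimuli at 15° by the end of 30 days of rehabilitation". Completion is also an absolute level, at 45°. No rule gives a hit count or names a reference run.
- **Use as an outcome.** Outcome Measure(s) makes Humphrey and the frame test primary for all participants, and makes change in VR results from visit 3 onward secondary. The exploratory tests are for subjects with restored fields.
- **Entry.** The selection criteria ask for a diagnosis and a lesion on imaging, with no required blindness at any angle.

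**The concern.** Expansion is a change, and a change needs a reference taken before treatment. The VR test has none in the text. It also has no trials on which a press must be wrong, so a subject's false-press rate is never measured. The setting invites presses: the test directly follows 200 button-press trials weighted 9:1 to the blind side, may be done at home, and has eye tracking only as an option.

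At stake are the routing decision, the VR secondary outcome, and the choice of subjects for the acuity, color and shape tests. If routing is wrong, those exploratory results describe a mixture of recovered and never-lost vision.

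**Working it through.** **1. The plan's own figure.** The only design calculation is the confidence interval under Sample Size: 1.96 × √(0.8 × 0.2 / 5) = 0.351, which matches the stated 0.35. It is not in dispute and does not bear on this point.

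**2. Trials per location.** 3 angles × 2 sides = 6 locations, and 30 / 6 = 5 trials each. The even split is an assumption. On that split, no trial is left over for a no-light presentation.

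**3. Guessing at one blind location in one session.** Let X ~ Binomial(5, f), where f is the chance of a press that scores as a hit. The documents give no f, so 10% and 20% are assumed, with independent presses.

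- P(X ≥ 3) = 10f³(1−f)² + 5f⁴(1−f) + f⁵
- P(X ≥ 4) = 5f⁴(1−f) + f⁵

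| f | at least 3 of 5 | at least 4 of 5 |
|---|---|---|
| 0.10 | 0.0081 + 0.00045 + 0.00001 = 0.0086 | 0.0005 |
| 0.20 | 0.0512 + 0.0064 + 0.0003 = 0.0579 | 0.0067 |

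The result depends on f and on a pass count that the plan does not state.

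**4. Spared vision.** With a true detection rate of 0.8 (assumed) and no treatment effect, the same formulas give P(X ≥ 3) = 0.2048 + 0.4096 + 0.3277 = 0.942 and P(X ≥ 4) = 0.737.

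**5. The rules applied to a subject who sees 15° at entry and does not improve.** The repeat rule does not apply, because the subject detects 15°. Session 33 does not apply, because there is no expansion. Session 63 does not apply, because there was no second round. The text leaves this subject without a route unless the spared vision is taken for expansion.

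**6. Change scores.** A constant level of sparing or guessing largely cancels in a change from the first VR run. A press rate that rises during training does not. At a blind location, going from f = 0.10 to 0.20 moves the expected hits from 5 × 0.10 = 0.5 to 5 × 0.20 = 1.0 of 5, and only no-light trials would reveal it.

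**7. How many no-light trials are needed.** After 0 presses in n such trials, the one-sided 95% upper bound on the press rate is 1 − 0.05^(1/n): 0.45 for n = 5, 0.26 for n = 10, and 0.02 for n = 150 (5 in each of 30 sessions). A single session says little; pooling is needed.

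**8. Noise in a single reference run.** Take two independent runs of 5 trials at an unchanged rate of 0.2. The second exceeds the first by 2 or more hits with probability 0.11 at one location, and 1 − (1 − 0.111)³ ≈ 0.30 at any of three. Looking only at locations missed at baseline adds regression to the mean. At a constant rate of 0.3, a run of 0/5 has probability 0.7⁵ = 0.17, and the next run gives at least 2/5 with probability 1 − 0.168 − 0.360 = 0.47.

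**The case against.** The strongest reply is that the primary comparison has its own safeguards. The frame test is run before training at 15°, 30°, 45°, 60° and 75°, with no-light trials. It covers every VR angle, and the ANOVA in the Analytical Plan is run on it. A false VR expansion sends a subject to that test and to Humphrey, where it would be rechecked. This stands, and it limits the point to the VR test and what hangs on it. Primary field data are at risk for subjects judged *not* improved, which is a conflict between the session 63 rule and Outcome Measure(s). While that conflict is open, a stricter VR trigger would send more subjects away from the field tests.

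Second, the session 3 run is close to a baseline. The background gives two weeks as the minimum for an effect, and the intervention section expects progress after 2–3 weeks. This is a fair argument, but the plan does not name that run as the reference.

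Third, lights come at random intervals, and presses between lights might expose guessing. No scoring window is described, however, so this check is not in the plan.

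Fourth, this is an exploratory study of 10 recruited subjects, so the fix must be cheap.

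Finally, the timeline figure was not available to me. A pre-training VR run shown only there cannot be excluded.

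**Conclusion.** The point holds for the VR test. The text gives it no pre-training run and no no-light trials, while using it for routing and as a secondary outcome. Per location and session, guessing is a small to moderate risk: 0.05% to 5.8% over press rates of 10–20% and pass counts of 3 or 4 of 5. Spared vision is the larger risk if expansion is judged by level: 94% at 3 of 5 and 74% at 4 of 5 for a true detection rate of 0.8. These figures rest on 5 trials per location, independence, and assumed press and detection rates.

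Three stronger readings are not supported.

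- **Treatment effect cannot be told apart from prior vision or guessing in this trial.** A reader might infer this, but the frame test has a baseline and no-light trials.
- **After restarts, the first VR run could follow weeks of training.** Study-related barriers says "The days since the start of rehabilitation will be reset to 0 once rehabilitation restarts", but it discards no earlier VR run. Because the test follows every session, a subject's first run always follows just one.
- **Guessing would nearly always succeed over 30 sessions.** The sum 1 − (1 − 0.0579)³⁰ = 0.83 needs a 20% press rate, a 3 of 5 criterion and a rule that one passing session at any time is enough. No such rule is stated: the repeat rule looks at the end of the 30 days, and completion asks for reliable detection.

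**What to change.** 1. At session 3, after brief headset familiarisation, run the VR progress test once before the first training trial. Keep that run, together with the pre-training frame test, as the reference, including after any restart.
2. Add 5 to 10 no-light trials to each VR test, and pool them over sessions to estimate each subject's false-press rate.
3. Report VR change from the pre-training value at all hemianopic locations, not only those missed at baseline. Average it over several late sessions and show it beside the false-press rate.

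**Cost.** One extra test of 2 to 5 minutes per subject and a small software change. The protocol gives both 2 and 5 minutes for the 30 trials, so a trial takes 120/30 = 4 s or 300/30 = 10 s. The added trials then take between 5 × 4 = 20 s and 10 × 10 = 100 s a day, or about one minute. A pre-training value that is not collected cannot be recovered later.

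**For the sponsor to reconcile.** The completion, repeat, session 33 and session 63 rules need to be reconciled with one another. So does the statement that the primary outcomes cover all participants with visits 63 and 64: session 63 lists questionnaires only, and no session 64 is described. The two stated test lengths also differ. No change to the routing or repeat rules is proposed here; the fix concerns measurement and reporting only.

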Auditory stimulus consists of a brief burst of white noise, lasting approximately 100 ms. Visual stimulus is a white colored orb positioned against the dark, neutral background and will be displayed for 1-2 seconds. The longer duration of the visual stimulus will serve to provide stimulus location feedback for patients. Patients will be instructed to orient their eyes and head toward stimuli in the hemianopic field and to push a button on a controller upon detecting stimuli. This part of the task will serve to boost motivation and maintain attention during training. The software will also record these responses and reaction times, based on the button presses, and store this data for later review. The next trial will begin 3-4 seconds after the visual or auditory-visual stimulus disappears and when the patient re-fixates on the fixation point.

Cross-modal visual auditory rehabilitation consists of a total of 200 trials / day (about 30 min) over 1 month. Given the results from animal model studies, we expect progress to be observable after 2-3 weeks of cross-modal rehabilitation, and completion of rehabilitation 1 month after the start of cross-modal training.

While we expect most patients will perform rehabilitation using the virtual reality rehabilitation system, patients may also complete rehabilitation with a free-field frame device if they are not comfortable with using a VR headset. The free-field frame device uses a semi-circular frame to hold LED lights (visual stimulus) and speakers (auditory stimulus) in front of the patient. These lights and speakers can be used to deliver the same cross-modal visual auditory rehabilitation paradigm. The device is also used to perform peripheral visual field tests, and is described in more detail below in *peripheral visual field test*.

Tests

Humphrey Visual Field (HVF) Test - The HVF test is a common test given to map the visual field. During the HVF test, light is projected into a white bowl with a standardized background light intensity to form a circular stimulus, around 30 cm away from the patient's eye. The overall field mapping technique used is a form of static perimetry, where a stimulus appears in various areas of the field of vision. The patient indicates when they can see the stimulus and the perimetrist then records the point where the stimulus was seen. These datapoints are used to determine the patient's visual field.

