Study Session 35: 3 Month Post-Intervention Follow-up Tests (1 hour)

Subjects will complete a follow-up visit 3 months after the end of rehabilitation on the Wake Forest Baptist Medical Center campus. The follow-up visit will consist of a peripheral visual field test, and NEI VFQ-25 and VA LV VFQ-48 questionnaires.

Study Session 36: 6 Month Post-Intervention Follow-up Tests (1 hour)

Subjects will complete a final follow-up visit 6 months after the end of rehabilitation on the Wake Forest Baptist Medical Center campus. The follow-up visit will consist of a peripheral visual field test, and NEI VFQ-25 and VA LV VFQ-48 questionnaires.

Outcome Measure(s)

The primary outcomes for all participants will be the visual field measurements from Humphrey Visual Field and peripheral frame test, with comparisons made before (visits 1 and 2) and after treatment (visits 34 and 35 or visits 63 and 64).

Secondary outcome measures will include differences in quality of life questionnaire results from before (visit 1) and after treatment (visit 33 or 63) and changes in VR progress test results during the course of rehabilitation (visits 3-32 and 33-62 if a subject repeats rehabilitation).

Exploratory outcome measures will be collected in subjects with restored visual fields. The qualities of recovered visual field will be examined with visual acuity, color recognition, and shape recognition tests after rehabilitation (visit 33 or 63).

Analytical Plan

Results will be analyzed initially using descriptive statistics. The improvement of visual detections will be assessed by using a two-way ANOVA on the percentages of visual detections to stimuli presented in the hemianopic hemifield in the peripheral visual field tests before and after rehabilitation. Comparisons for subjects will be done using chi square tests for proportions, and t-tests or ANOVA procedures for continuous variables. Other inferential statistical analysis will be conducted as appropriate.

Human Subjects Protection

Subject Recruitment Methods

Protocol version: 2

Protocol updated 7.01.20

Subjects with homonymous hemianopia on either the left and right side of the visual field will be recruited using resources from Wake Forest University Health Sciences' Clinical and Translational Science Institute (CTSI). Members of the PI's research team will perform recruitment. Coordination of potential participants' visit will be done by phone or in person conversation or by email.

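### A one-month course and an undefined 45° completion rule are not reconciled; if the 45° rule ends training, the VR secondary outcome is cut off at its own favourable values

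*Combined protocol and SAP*

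**What the plan says.** All references are to the combined protocol and SAP.

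**A fixed course.** The Interventions section states: "Cross-modal visual auditory rehabilitation consists of a total of 200 trials / day (about 30 min) over 1 month". It expects "completion of rehabilitation 1 month after the start of cross-modal training". The schedule lists Sessions 3–32, which is 30 sessions, as "Cross-Modal Rehabilitation Training (30 minutes each day".

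**A performance criterion.** The text under Sessions 3–32 states: "The rehabilitation will be considered complete once patients can reliably detect stimuli 45° in the hemianopic field". It gives no threshold, number of sessions or instrument. The sentence just before it introduces the VR test: "At the end of each rehabilitation session, subjects will perform a brief 2-minute VR visual field progress test with the VR system".

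**A repeat rule.** The next paragraph adds: "If patients cannot detect stimuli at 15° by the end of 30 days of rehabilitation, they will repeat the rehabilitation for one more month". A subject who detects 15° but not 45° at day 30 meets neither this rule nor the completion rule.

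**The VR test.** Under Tests: "The test consists of 30 trials with visual stimulus presented either 15°, 30°, 45° in either the hemianopia field or the intact field".

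**Its role as an outcome.** Outcome Measure(s) lists as secondary "changes in VR progress test results during the course of rehabilitation (visits 3-32 and 33-62 if a subject repeats rehabilitation"). No end value is named. The text for Sessions 33 to 36 and 63 schedules no further VR progress test. The primary outcomes are the Humphrey and peripheral frame tests.

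**The concern.** One rule for course length runs on the calendar and the other on performance, and nothing says which governs. This matters statistically because the test that most plausibly triggers the second rule is also a secondary outcome.

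If training ends when the criterion is met, two things follow. First, a subject's last VR reading is one that helped to meet the criterion. It was selected for being high, on a handful of trials, after as many as 30 chances, and no later VR reading corrects it. Second, the VR series is shortest in the best scorers, so any summary by visit over Sessions 3–32 comes to describe slower subjects only. The second effect needs no chance success at all.

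At stake is the VR change that would inform later studies. With the 5 completers hoped for under Sample Size, one subject wrongly counted as complete is 1/5 = 20% of the data.

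**Working it through.** **The plan's own figure.** The completion rule has no stated error rate. The only design figure is the precision under Sample Size: 1.96 × √(0.8 × 0.2 / 5) = 0.351, which reproduces the stated 0.35. It does not bear on this rule.

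**Inputs from the plan**
- VR test: 30 trials over 3 eccentricities × 2 sides = 6 positions.
- One test after each of 30 sessions, so up to 30 looks per round.

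**Assumptions (not in the plan)**
- Equal split, so 30/6 = 5 trials at the hemianopic 45°. If each position were drawn at random, the 95% range is about 1 to 9.
- True detection rate p is constant (no training effect) and sessions are independent.
- The VR test decides completion, training stops there, and the last reading is the end value.
- *Reliably* is read in three ways: 4 or more of 5 in one session; 5 of 5 in one session; 4 or more of 5 in two consecutive sessions.

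**How little one session tells.** The exact 95% interval for 4/5 is 0.28–0.99, and for 5/5 it is 0.48–1.00.

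**One-session rules.** With X ~ Binomial(5, p), a session passes with probability q = P(X ≥ r). The chance of at least one pass in 30 is 1 − (1 − q)^30. The mean last value is that chance times the mean of a passing session, plus the remainder times the mean of a failing one.

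Example, p = 0.3 and r = 4:
- q = 5 × 0.3⁴ × 0.7 + 0.3⁵ = 0.02835 + 0.00243 = 0.0308
- chance of a pass = 1 − (1 − 0.0308)^30 = 0.609
- mean of a passing session = (0.8 × 0.02835 + 1 × 0.00243) / 0.03078 = 0.816
- mean of a failing session = (0.3 − 0.02511) / 0.96922 = 0.284
- mean last value = 0.609 × 0.816 + 0.391 × 0.284 = 0.608, a bias of +0.31

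Simulation of 200,000 subjects per setting agrees.

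**Two consecutive passes.** The probability a_n of no such pair in n sessions follows a_n = (1 − q)a_(n−1) + q(1 − q)a_(n−2), with a_0 = a_1 = 1. The chance of completion is 1 − a_30. The mean last value is from simulation.

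Each cell gives the chance of being declared complete with no true change, then the bias in the last value:

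| True rate | 4 of 5, one session | 5 of 5, one session | 4 of 5, two consecutive |
|---|---|---|---|
| 0.05 | 0.1%; +0.00 | 0.0%; +0.00 | 0.0%; +0.00 |
| 0.10 | 1.4%; +0.01 | 0.03%; +0.00 | 0.0%; +0.00 |
| 0.2 | 18%; +0.11 | 1.0%; +0.01 | 0.1%; +0.00 |
| 0.3 | 61%; +0.31 | 7%; +0.05 | 2.6%; +0.01 |
| 0.4 | 93%; +0.39 | 27%; +0.155 | 18.5%; +0.08 |
| 0.5 | 99.8%; +0.33 | 61%; +0.30 | 59%; +0.19 |

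A reading that plays no part in the decision has expected value p, so its selection bias is 0.

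**The case against.** Much of the chain is inferred. The text requires reliable detection and nowhere says that one session is enough; the word points the other way. The VR test is linked to the criterion only by the order of the sentences. *Complete* could label success rather than stop training. Most of the plan reads as a fixed course: the month in Interventions, the 30 scheduled sessions, the day-30 check, and the restart of the full 30 days after missed sessions under Study-related barriers. If every subject trains for the full course, there is no selection and no shrinking series. Nor does the plan name a last-value summary; the VR outcome could be analysed as a trajectory.

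These points stand, and they make the size conditional. They do not remove the conflict. No other detection test is scheduled during training, and the text for Sessions 33 and 63 explicitly uses VR results to decide which visit a subject has, so the VR reading of the rule is the natural one. A stricter meaning of *reliably* reduces the bias without always removing it: two consecutive passes still give +0.19 at a true rate of 0.5.

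A reader might infer that a single lucky session will end training and that a subject whose field stays blind will be recorded as recovered. The documents do not support that. The first part is not stated, and at rates of 0.10 or below even the most permissive rule examined passes at most 1.4% of unchanged subjects. Material bias needs partial detection at 45° already, through incomplete loss or false presses.

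**Conclusion.** The point holds as a need for reconciliation, with a conditional consequence for one secondary outcome. The course-length and completion statements conflict, and *reliably* and the VR end value are undefined. Only if training ends on the 45° criterion, decided by the VR test, is the VR series truncated on its own favourable values.

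Under the assumptions of 5 trials, 30 independent looks, no true change and the last reading as end value, the bias runs from about 0 in a near-blind field to roughly +0.4 with partial detection and a one-session 4-of-5 rule. That range reflects what the plan leaves unsaid; it is not an estimate of what will happen. The composition change across visits arises under the same reading, but the documents give no basis for sizing it.

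It would be tempting to conclude that the trial's efficacy result is inflated. That does not follow. The primary outcomes come from separate tests and are not directly biased by this selection, although the amount of training could differ between subjects. In an exploratory study this is a low-cost improvement, not a threat to the main result.

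**What to change.** 1. Reconcile the one-month statements with the 45° completion sentence. Say whether meeting the criterion ends training, which test decides it and what *reliably* means, and cover the subject who detects 15° but not 45° at day 30. These are the sponsor's decisions.
2. If training can end on the criterion, add one VR progress test at the end-of-training visit (Session 33 or 63) for every subject able to use the headset. It must play no part in deciding completion. Name it as the end value of the VR secondary outcome.
3. In that case, also show VR results session by session with the number of subjects still in training at each visit.

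If the fixed month stands for everyone, the extra test is not needed for this reason.

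Cost: one more run of an existing test per subject (the plan gives its length as 2 minutes in one place and 5 in another) and a few lines of outcome wording. The reported VR gain may be smaller. A single fresh reading still rests on about 5 trials at 45°, so it removes the selection but remains imprecise; the session-by-session display should accompany it.
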